A limiting factor in the use of epidural analgesia, however, is the high incidence of associated hypotension. Hypotension is defined as systolic blood pressure (SBP) > 20% below the baseline preoperative measurements and acquired before the epidural or any sedation has been administered. Effective segmental epidural block would thus invariably cause sympathectomy due to its location in the thoracic or lumbar areas by blocking the cardiac sympathetic nerves, the pre-ganglionic nerves to the adrenal glands or the sympathetic nerves to the blood vessels individually or in combination.

It has been proven beyond doubt that epinephrine, when added to ropivacaine 0.2% and used for epidural analgesia by infusion, is safe and may even improve spinal cord blood flow and the analgesic effects of ropivacaine.⁷ It is also known that the cause of hypotension associated with epidural analgesia is the blockade of the sympathetic outflow to the cardiovascular and adrenal systems, and that the ideal mechanism to counter this would be by beta1-stimulation, which is ideally achieved with low-dose epinephrine.

Finally, it is known that epidural infused epinephrine increases its serum concentration.⁸ What is not known is whether added epinephrine will counteract this sympathetic blockade and prevent hypotension, and what the optimal concentration of epinephrine infusion would be during epidural analgesia with 0.2% ropivacaine to achieve optimal analgesia and optimal hemodynamic status.

5. Specific Aims:

We aim to examine whether adding epinephrine will counteract the sympathetic blockade and prevent hypotension, and what the optimal concentration of epinephrine infusion would be during epidural analgesia with 0.2% ropivacaine that can achieve both optimal analgesia and optimal hemodynamics. Specifically we plan to answer the following questions:

- 1. Does the addition of epinephrine to the epidural infusion of 0.2% ropivacaine:
 - a. Prevent hypotension?
 - b. Lead to a wider spread of local anesthetic effect?
 - c. Lead to a difference in the average pain scores?
 - d. Lead to a difference in when ambulation occurs?
 - e. Decrease potential of other opioid-related side effects such as pruritus, nausea/vomiting, respiratory depression and opioid consumption?
- 2. What is the optimal concentration of epinephrine (2mcg/mL or 5mcg/mL) to achieving the above-mentioned outcomes?

6. Research Plan:

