Activity	Screen	Pre-op (baseline)	Pre-op after epidural, before bolus	Pre-op after epidural, after bolus/before anesthesia	Intra-op	Post-op Recovery (PACU)	1 hour post-op	Transfer to floor	POD 1	POD 2	POD 3
Informed consent	Х										
Inclusion / Exclusion Criteria	Х										
Medical History	Х										
Randomization		Х									
IV Placement		Х									
Primary measurements(SBP,DBP,MAP, HR,SaO2,RR,Pain score?) every 3-5 min		х	х	х	х						
Epidural Placement		Х									
Administration of Pre-op sedation			х								
Prep and supply of test drug			Х								
Infusion of Study drug if randomized for test group				х							
Infusion of Ropivacaine				х							
Primary measurements every 15 min						х	х				
(Secondary measurements) Sensory block assessment (1 hour post-op and every 6 hours for the subsequent 72 hours						x	х		x	x	x
Intra-op surgical records					Х						
Anesthesia Pain Service records			х	х	х	х	х	х	х	х	х
Pain Scores DVPRS Score							Х		Х	Х	Х
Record 24 hour I/Os						Х			Х	Х	Х
Pain management and "Rescue Drug" administration as needed							х	х	х	х	х
Record opioid usage						Х	Х	Х	Х	Х	Х
All SOC points and monitors: EKG, non-invasive BP; ETCO2; pulse ox; arterial line with Flow Track (if indicated); peripheral or central venous line; induction and mode of anesthesia.		x									
Physical therapy rehabilitation records (Time and distance of ambulation)									x	х	х

Patients will be approached about their willingness to participate in this study either in a pre-operative surgical or anesthetic clinic visit or in the pre-operative area on the day of surgery. Consent will be obtained by a member of the research team. The patient will be given time to read the consent, have all study related questions answered, and discuss the study with their family, if desired. A copy of the signed consent will be placed in the patient's physical chart, and a research progress note documenting study enrollment will be made in the patient's electronic medical record.

Inclusion criteria:

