Patients will receive a bolus of 500 mL of 5% Albumin intravenous infusion as per the usual routine practice of the APS before the main bolus dose is injected. A preoperative level of block will be established that is appropriate for the surgery by injecting an appropriate volume of ropivacaine 0.5% or lidocaine 2% w/ epinephrine 1:200,000 (5–10 mL) into the epidural space as per the usual practice of the APS. This will be done after the routine test dosing with 3 mL of 2% lidocaine and 1:200,000 epinephrine, confirmed that intrathecal and intravascular markers are negative. If an insensate-to-cold area in the appropriate dermatomes cannot be established within 10 minutes following a 5 to 10 mL (maximum 10 mL) injection of ropivacaine 0.5%, the epidural catheter will be removed and replaced. If this process is repeated and there was still no level, it will be annotated and the patient will be removed from the study, labeled as a primary block failure, and treated appropriately by the attending anesthesiologist by either repeating the epidural block placement a third time or using other appropriate perioperative analgesia.

Research-Related Procedures - Preoperative Period:

Once consent is obtained, patients will be randomly allocated by computergenerated randomization to one of four groups. This will be a quintuple blinded prospective study. The anesthesiologist managing the intraoperative anesthesia, the anesthesiologists (APS) placing the blocks and following the patients on the floors, the research nurse taking the measurement, the surgeons, nor the patients will be aware of what combination of drugs are used for the epidural block infusion.

The three groups will consist of:

- 1. Group A (Ropivacaine 0.2% infusion; Control group)
- 2. Group B (Ropivacaine 0.2% + 2 mcg/mL epinephrine)

3. Group C (Ropivacaine 0.2% + 5 mcg/mL epinephrine)

The pharmacists will make up and supply test drugs for groups A, B and C and provide them labeled to the block area drug dispenser as "A, B, or C test solutions" without specifically identifying the content.

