Immediately following the establishment of an appropriate level for the planned surgery, an infusion of the test drug will be initiated at 4 to 8 mL per hour with a 4- to 8-mL patient-initiated bolus at a lockout interval of 1 hour – typically 8 mL per hour for major abdominal or thoracic surgery and thoracic epidural placement and 4 mL per hour for hip arthroplasty and lumbar epidural. Once established as effective for the clinical situation, this infusion will be left unchanged throughout the surgery and postoperative period. If clinically indicated, and the infusion rate is changed to below the limits of 4 – 8 mL per hour, this indicates the end of the need for the epidural infusion or otherwise untreatable hypotension.

Standard of Care - Intraoperative and Postoperative Periods:

Intraoperative and postoperative fluid management will be at the discretion of the anesthesia and primary teams.

Preoperative sedation will be a maximum of 5 mg of midazolam by intravenous injection (IV) and alfentanil 2000 mcg IV. Monitors include: EKG, non-invasive blood pressure, ETCO2, pulse oximeter, arterial line with Flow-Track (if indicated and appropriate per intra- or postoperative operative anesthesiologist), peripheral intravenous or central venous line as deemed appropriate by the attending intra- or postoperative operative anesthesia and mode of anesthesia (maintenance, fluid management, intraoperative analgesia, muscle relaxation, etc., are at the discretion of the attending intraoperative anesthesiologists.

If hypotension (see definition below) is encountered intraoperatively, the attending anesthesiologist will start a vasoactive or positive inotropic medication as indicated by the patient's medical requirements.

Research-Related Procedures – Intraoperative:

- Anesthesiologists will be encouraged to use alpha agonists if the other causes of hypotension are excluded and lumbar epidural is judged to be a contributory cause of the hypotension; and epinephrine, dobutamine, or dopamine (or indirect inotropic agents such as ephedrine) if thoracic epidural is judged to be the cause of the hypotension and the other causes of hypotension such as hypovolemia have been ruled out.

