- The epidural infusion will be continued intraoperatively at a rate 4 to 8 mL per hour. Emergence medications will be administered and recorded as judged appropriate by the intraoperative anesthesiologist. A bolus of 5 mL of ropivacaine 0.5% without additives may be administered through the epidural catheter at the conclusion of the intraoperative phase by the intraoperative anesthesiologist or APS anesthesiologist in the recovery room, if required.
- "Rescue" drugs as outlined below will be administered and recorded if deemed necessary. If, after sensation level testing, the epidural block was not appropriately covering the area of surgery, a further bolus of 5 mL of 0.5% ropivacaine will be injected by the APS physician and if this was still not managing the pain, this will be noted and the patient will be removed from the study. If judged appropriate by the APS physician, the epidural will either be replaced in the recovery area or the "rescue" medication described below will be initiated.
- Hypotension is defined as SBP > 20% below the baseline in the block room area before the epidural or sedation for the epidural was administered or an MAP less than 55 mmHg. Epidurals will be turned down or turned off if the treating Intensive Care Primary Physician declared it an emergency, if the patient had hemodynamic instability stemming from other causes that was complicated by the sympathetic block of the epidural, or significant hypotension, or mean MAP <

30%, from baseline and other causes such as hypovolemia had been corrected. If this is the case, the patient will be removed from the study.

Research-Related Procedures - Postoperative Periods:

If additional pain management or "rescue" analgesics are needed, for example, from outside the area covered by the epidural; subjects may receive any of the following:

- Acetaminophen (Tylenol) 1000 mg scheduled intravenously every 8 hours for the first 48 hours and, after oral intake is restarted, it will be changed to 1 gram every 6 hours by mouth (patients with liver disease will be excluded if appropriate and after discussion with the hepatic surgeon)
- Ketorolac Tromethamine (Toradol) 30 to 60 mg every 6 hours intravenously
- Celecoxib (Celebrex) 100 mg per mouth every 12 hours
- Oxycodone 5 to 10 mg per mouth every 4 hours as needed
- Intravenous hydromorphone (Dilaudid) patient-controlled analgesia (PCA) as per APS routine protocol appropriate for age and body habitus of the patient.

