Primary measurements:

Include the average invasively or non-invasively measured SBP, diastolic blood pressure (DBP), MAP, arterial blood oxygen saturation (SaO2), heart rate, respiratory rate, and pain by the visual analog pain score (VAS) on the "Defense and Veterans Pain Rating Scale" (DVPRS) measured over the following set periods:

Preoperative period

Primary measurements every 3 to 5 minutes and at indicated time points:

- I. Before the bolus epidural is injected.
- II. After the epidural bolus is injected but before anesthesia is induced.

Intraoperative period

Primary measurements every 3 to 5 minutes

Postoperative period

I. Primary measurements in the recovery room (if appropriate) every 15 minutes

II. Primary measurements following transfer to the floor every 4-6 hours if within normal limits, but every hour if needed for closer observation in case of possible abnormality for as long as the epidural analgesic blocks are continued, but at least every 8 hours after discharge from the PACU.

Secondary measurements:

[figure not shown]
- III. Spread of block per spinal root segment as tested by sensitivity to cold recorded every hour postoperatively and every 8 hours for the subsequent 72 hours after discharge from the PACU.
- IV. Ambulation on the first day after surgery (POD 1), POD 2 and 3, will be recorded per physical therapy protocol and distance ambulated per 24hour period will also be recorded. Physical Therapy information will be gathered to test motor effect on lumbar epidurals.
- V. Opioid usage data will be recorded and converted to morphine equivalents and averaged for POD 0, 1, 2, and 3 per group.
- VI. Side effects such as pruritus, nausea/vomiting, and respiratory depression (defined as respiratory rate less than 10 breaths per minute of oxygen saturation more than 7 points lower that the patients preoperative value on room air) will be recorded and managed as deemed appropriate by the attending physician.
- VII. 24 hour I/O for the first 72 hours to assess fluid balance, length of stay, and amount of days before return to PO status.

Data analysis plan

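### The plan does not fix whether sensory spread (Aim 1b) is recorded before or after clinician epidural boluses, so early post-operative readings can be diluted toward no difference

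*Combined protocol and SAP*

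**What the plan says.** Section 5 (Specific Aims), question 1b, asks whether adding epinephrine will "Lead to a wider spread of local anesthetic effect". Spread is listed under Secondary measurements.

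**Before the study drug.** Under Standard of Care - Preoperative Period, "A preoperative level of block will be established that is appropriate for the surgery", using non-study local anaesthetic and a cold test in the relevant dermatomes. Then: "Immediately following the establishment of an appropriate level for the planned surgery, an infusion of the test drug will be initiated".

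**After surgery.** Research-Related Procedures - Intraoperative describes two clinician boluses.
- Optional: "A bolus of 5 mL of ropivacaine 0.5% without additives may be administered through the epidural catheter", at the end of the intraoperative phase or in the recovery room, if required.
- Coverage-triggered: if sensation testing shows that the block does not cover the surgical area, "a further bolus of 5 mL of 0.5% ropivacaine will be injected by the APS physician". If pain is still not managed, the patient leaves the study.

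**Recording of spread.** The schedule table in section 6 marks recovery, 1 hour post-op and POD 1 to 3, with the label "Sensory block assessment (1 hour post-op and every 6 hours for the subsequent 72 hours". Secondary measurements gives a different schedule: "Spread of block per spinal root segment as tested by sensitivity to cold recorded every hour postoperatively and every 8 hours" for 72 hours after PACU discharge.

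**Analysis.** The Data analysis plan names mixed models for continuous primary outcomes and logistic regression for categorical ones. It names no model for spread and says nothing about clinician boluses. Bolus use is not a listed outcome.

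**The concern.** The coverage bolus is triggered by a finding closely tied to what Aim 1b measures. If epinephrine widens the block, more control patients should fail the coverage test. More of them would then have the block extended with a drug other than the study infusion. A spread reading taken after that bolus reflects the bolus as well as the randomised solution, and the arms move closer together.

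Removal works in the same direction. Patients who still fail after the bolus are likely to include the narrowest blocks, and under this hypothesis more of them come from the control arm.

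At stake is a diluted answer to Aim 1b in the early post-operative period. The two quantities that would reveal the mechanism, bolus need and removal by arm, have no planned comparison.

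**Working it through.** **The plan's own figure.** No effect size or sample size is given for spread. The nearest is Cohen's f = 0.24 for group means, at 80% power, alpha 0.05 and n = 200 (50 per group). One-way ANOVA with noncentrality f² × N:
- Four groups: 0.0576 × 200 = 11.52, power 0.815. The figure reproduces (exact f for 80% power is 0.236).
- Three groups of 50, as listed: 0.0576 × 150 = 8.64, power 0.743, detectable f 0.256.

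The three-versus-four-group conflict is a separate matter. This check says nothing about spread.

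**Order of events, from the text.**
1. Non-study drug sets the level in every arm, and the study infusion then starts. A pre-infusion reading cannot show the study drug's effect but can serve as a baseline.
2. An optional bolus may follow at the end of surgery or in recovery. No test is required before it.
3. A sensation test is done. If coverage is inadequate, the coverage bolus is given.
4. Spread is recorded in recovery and at 1 hour. No rule links this record to steps 2 or 3. The recorded value could be the step 3 test, or a later one.

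**Illustration of one early reading taken after the coverage bolus (all inputs assumed).** SD 3 segments, means 8 (control) and 10 (epinephrine), bolus given below 7 segments, bolus adds 3 segments.
- Bolus given: Φ((7 − 8)/3) = 0.369 and Φ((7 − 10)/3) = 0.159.
- Recorded difference: 2 − 3 × (0.369 − 0.159) = 1.37 segments, a loss of 0.63/2, about 32%.
- Thresholds 6, 7 and 8 with gains of 2 or 3 segments give differences from 1.68 down to 1.26, a loss of 16% to 37%.

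**Second set of assumptions, by simulation.** Two arms of 50. The true difference is set at (1.960 + 0.842) × √(2/50) = 0.56 SD, which gives 80% power without boluses. SD is 2 or 3 segments, and 10% to 50% of control blocks fall below target.

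| Handling of blocks below target | Share of true difference kept | Power |
|---|---|---|
| Bolus adds 2 segments | 62% to 92% | 0.71 to 0.79 |
| Raised exactly to target | 60% to 94% | 0.70 to 0.80 |
| Bolus adds 2 segments; those still below target removed | 42% to 87% | 0.46 to 0.76 |

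**Over the whole follow-up.** Assume two recovery readings and nine 8-hourly readings (72/8 = 9), 11 in all, and suppose one bolus alters 1 to 3 of them. A 32% loss on each altered reading averages to 32% × 1/11 = 3% up to 32% × 3/11 = 9%. The documents do not give the duration of the bolus effect.

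**Limits of the model.** The calculations trigger on the number of segments, whereas the protocol triggers on coverage of the surgical area, which also depends on where the block lies. The protocol removes patients for unmanaged pain, not for a segment count. The figures show direction and plausible scale only.

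**The case against.** A reader might infer that the boluses have already widened the narrow blocks before spread is first recorded, and so hide any difference. The documents do not support that.
- The coverage bolus follows a sensation test, and the scheduled recovery reading could be that test.
- The other bolus is optional and not tied to a narrow block. The statement that no additives are used is written for that bolus only.
- Blocks that already cover the area do not trigger the coverage bolus. Spread is followed for 72 hours, and the infusion, once established as effective, is left unchanged. Dilution of early readings is the supportable claim.

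Starting the spread record after surgery is not itself a fault, because the pre-operative level is set before the study drug begins.

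Two further objections also stand. Bolus amounts and times appear to be captured already: section 7 lists drug amounts and administration times among the data, and the schedule table collects Acute Pain Service records from before surgery to POD 3. What is missing is a planned comparison. In addition, a recovery test cannot precede a bolus given at the end of surgery unless that bolus is delayed, so a rule demanding that order would intrude on clinical management.

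These points limit the size and the remedy, but they do not supply the missing order. The plan does not say that the pre-bolus test is the recorded value, names no main time point for Aim 1b, and leaves removals outside any stated analysis.

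**Conclusion.** The concern holds in a limited form. The order of spread recording and clinician boluses is unspecified, and no analysis accounts for boluses or removals. Early post-operative readings can therefore be biased toward no difference if epinephrine does widen the block, and removals can add to the bias. Later readings are probably less affected.

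The size cannot be derived from the documents, which give no mean, SD, target level or bolus rate for spread. The 16% to 37% loss rests on assumed inputs and applies to a single reading taken after the boluses. The assumed 37% versus 16% bolus rates are likewise a product of the inputs. That 21-point gap is below the 26-point difference the plan says it can detect, so bolus need by arm would be informative rather than decisive.

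Severity is minor to moderate, because spread is a secondary measurement. The conflict between the 6-hour and 8-hour schedules is plain on the text and needs no assumption.

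**What to change.** None of these changes alters when or whether a bolus is given.

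1. Record, as the Aim 1b recovery value, the sensation test that already precedes the coverage bolus. Flag every spread reading as before or after any clinician bolus, including one given at the end of surgery. Prespecify a sensitivity analysis that accounts for post-bolus readings. Simply deleting them would discard information from the patients whose blocks fell short.
2. Report by arm, as a secondary outcome, the proportion needing a clinician bolus (with time) and the proportion removed for inadequate block. Use the drug administration and Acute Pain Service records already collected.
3. Name the model for spread. Record the pre-infusion cold level, already tested to accept the block, in segments and use it as a covariate. This is for precision, since loading drug and volume vary.
4. Reconcile the spread schedule between the section 6 table (1 hour, then every 6 hours) and Secondary measurements (hourly, then every 8 hours).

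Cost: one or two form fields, a few sentences in the protocol and a little more analysis.

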Up to 250 patients between the ages of 18 and 80 years undergoing epidural analgesia to treat perioperative pain associated with major surgery will be approached for their willingness to participate in the study. Patients undergoing major thoracic, abdominal, urological or orthopaedic surgery for whom thoracic or lumbar epidural block would be indicated and planned for intraoperative and postoperative analgesia as per the UF Acute Pain Service (APS) usual and routine practice will be included in this study. Our epidural failure rate is lower than 20% and our institution performs around 100 epidurals a month. If only a 1/3 of our patients agree to be part of our study we would have 24 study patients a month. This would then mean that our study would take 10 months to complete data collection.

Exclusion criteria:

Sepsis (febrile, above normal and upward trending white blood count, and/or positive cultures for systemic infection), patients with acute trauma, coagulopathy [INR >1.4, platelets < 100,000, and/or anticoagulation medication given out of UF APS adaptation of the American Society of Regional Anesthesiologists (ASRA) guidelines⁹, preoperative hemodynamic instability, symptomatic coronary artery disease (angina etc.), patients from the ICU whose tracheas were intubated for any cause, patient refusal, pregnancy, allergies to medications in the protocol, and primary or secondary block failure.

Standard of Care - Preoperative Period:

All patients will receive a standardized continuous epidural block at the appropriate level for the planned surgery by the APS physician staffing the block room that day. For the standardized continuous epidural block, placement will be confirmed with loss of resistance technique (LORA), wave form analysis or nerve stimulation.

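### Patients stopped for hypotension or failed block after randomisation leave the study, and the analysis plan has no analysis set or rule for their data

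*Combined protocol and SAP*

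**What the plan says.** All places are in the combined protocol and SAP.

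- **Timing.** Research-Related Procedures, Preoperative Period: "Once consent is obtained, patients will be randomly allocated". Study infusion starts later, when a suitable block level has been established.
- **Removal for haemodynamic reasons.** Research-Related Procedures, Intraoperative, hypotension bullet. The epidural may be turned down or off for a declared emergency, for instability from other causes made worse by the block, for significant hypotension, or on a MAP criterion, when other causes "such as hypovolemia had been corrected. If this is the case, the patient will be removed from the study".
- **Removal for block failure on study drug.** Same section, rescue bullet. If testing shows that the block does not cover the surgical area, a further bolus is given, and "if this was still not managing the pain, this will be noted and the patient will be removed from the study".
- **Exclusion criteria.** The list ends with "patient refusal, pregnancy, allergies to medications in the protocol, and primary or secondary block failure". Secondary failure can only be known after randomisation.
- **Stop for effects attributed to epinephrine.** Possible Discomforts and Risks has the epidural turned off and the pharmacy asked for the dose. It does not say how these patients are analysed.
- **Data analysis plan.** Mixed models are named for continuous outcomes and logistic regression for incidence of hypotension. No analysis set is defined. Nothing says whether data before removal are kept, or whether a stop for hypotension is an event. The one remark on missing data describes mixed models.

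**The concern.** Aim 1 asks "whether adding epinephrine will counteract the sympathetic blockade and prevent hypotension". One route out of the study is a severe form of that same outcome. The other route depends on block coverage (Aim 1b) and pain (Aim 1c, and pain is also among the primary measurements).

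If patients who leave by these routes are dropped, selection happens after randomisation and on the outcome. Equal removal across arms costs some power. Unequal removal biases the odds ratio. The remark on mixed models does not help the logistic model for hypotension. Even for the mixed models, it does not say who is analysed or whether earlier readings stay.

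Primary block failures are different. They occur before study infusion starts and under blinding, so leaving them out is not the problem.

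**Working it through.** **Inputs from the documents:** 80% power, alpha 0.05 (two-sided assumed), n = 200 stated as 50 per group, a detectable difference of 26% in incidence, an epidural failure rate below 20%, and up to 250 patients approached. Three groups are listed although 50 per group implies four, so results are shown at 50 per arm and at 200/3, about 67 per arm.

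**Assumed, because the documents give no figure:** hypotension incidence of 50% in control and 24% in one epinephrine arm (26 points apart), and every removal rate for hypotension.

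**Step 1: the plan's figure.** A two-proportion test with pooled variance under the null and 50 per arm detects 24.8 points from a control rate of 40%, and 26.7 points from 50%. The stated 26% lies between these. At 50% v 24%, power is 78% with 50 per arm and 88% with about 67.

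**Step 2: dropping hypotensive patients.** Suppose a fraction r of hypotensive patients in an arm is removed and their events are lost:

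- observed incidence = p(1 − r)/(1 − pr)
- arm size = n(1 − pr)
- observed odds ratio = 3.167 × (1 − r_control)/(1 − r_epinephrine)

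Worked case, r = 10% in control and 5% on epinephrine, 50 per arm:

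- Control: 0.45/0.95 = 47.4%, arm size 50 × 0.95 = 47.5.
- Epinephrine: 0.228/0.988 = 23.1%, arm size 50 × 0.988 = 49.4.
- Odds ratio: 3.167 × 0.90/0.95 = 3.00. Power 71%.

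| Removed, control/epinephrine | Odds ratio | Power, 50 per arm | Power, about 67 per arm |
|---|---|---|---|
| none | 3.17 | 78% | 88% |
| 10%/10% | 3.17 | 75% | 86% |
| 10%/5% | 3.00 | 71% | 83% |
| 20%/10% | 2.81 | 64% | 76% |

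**Step 3: keeping earlier events.** If a share k of removed patients have their event kept, r becomes r(1 − k). With k = 1, r is 0 and the first row of the table applies: no loss on incidence.

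**Step 4: block failure unrelated to outcome.** The recruitment text says: "Our epidural failure rate is lower than 20% and our institution performs around 100 epidurals a month". The rate is not split into primary and secondary failure, so 20% is an upper bound for removals on study drug. At 20% removed in both arms, 50 × 0.80 = 40 per arm gives 68% power, and 66.7 × 0.80 = 53.3 per arm gives 80%. The odds ratio does not change. If the ceiling of 250 is an allowance for failures, 250 × 0.80 = 200 and that power loss disappears.

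**The case against.** The strongest reply is that the text never orders events to be deleted. Leaving the study could mean only that study drug stops. Blood pressure is taken every 3 to 5 minutes in theatre and every 15 minutes in recovery, and the endpoint definition is milder than the trigger for stopping. Most patients removed for hypotension would therefore already have a recorded event. Turning down also looks like a last resort, so removals may be few, and small or equal removals do little harm. All of this stands. It limits the likely damage but does not supply the missing rule, and floor readings are sparser.

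Three stronger readings are tempting and are not supported.

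- **That the protocol discards hypotension events.** It leaves the matter open.
- **That the bias is large or has a known direction.** Large effects need high assumed removal rates with all events lost, and no rate is given. The Background does say that epinephrine "may even improve spinal cord blood flow and the analgesic effects of ropivacaine", which might suggest more pain removals in control. But removal also requires inadequate coverage and a failed further bolus, and the planned mixed models can use earlier readings. The documents do not allow that effect to be sized.
- **That block failure must cost up to a fifth of the sample.** The 250 ceiling may be meant to cover it. The documents do not say so, 250 is the number approached, and replacing patients would not cure selection.

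**Conclusion.** The point holds as a defect in the rules for who is analysed and which data count. The protocol takes patients out after randomisation for reasons tied to Aim 1a and partly to Aims 1b and 1c, and the analysis plan does not say what happens to them or their data. It should be settled before any analysis by arm, because a rule chosen after seeing the data would not be credible and readings not collected after a stop may be lost.

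Confidence is high on the removal rule and the missing analysis set. It does not extend to the size or direction of bias. Under the assumed 50% v 24%, with removed events dropped, the cases shown run from an unchanged odds ratio and about 3 points of power (equal 10% removal) to an odds ratio of 2.81 and 64%/76% power (20%/10%). With all earlier events kept, the loss on incidence is nil.

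**What to change.** Leave every clinical rule on turning down, stopping and rescue as it is. Change the wording on data and analysis:

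- **Research-Related Procedures, Intraoperative.** For events after study infusion starts, replace removal from the study with a statement that the change or stop and its reason are recorded and the patient stays in the analysis.
- **Exclusion criteria.** Delete secondary block failure.
- **Data analysis plan.** State that every randomised patient who started study infusion is analysed in the assigned group, including those stopped under Possible Discomforts and Risks. State that all readings and events before the change are kept, and that a turn-down or stop for hypotension counts as a hypotension event. Report stops by arm and reason. Show the analysis without these patients only as a sensitivity analysis.
- **Primary measurements.** State that routinely charted blood pressure and pain scores continue to be abstracted after a stop. The floor schedule is now tied to the epidural continuing, and its 8-hourly minimum has no stated end.

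The cost is a few sentences and a little more chart abstraction. Retained failed blocks may dilute the effect slightly. Randomisation timing and patient care do not change.
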